**Infective Complication due to Immunosuppressive treatments**

To address the risk of opportunistic infections and organ toxicity due to combined steroid and tacrolimus treatment, periodic clinical, biochemical (full blood count, renal and liver function) drug level (FK506), immunological and virological monitoring (PCR for cytomegalovirus-CMV and Epstein virus-EBV) will be instituted at fixed intervals (see details in the specific chapter) and depending on patient's clinical and biochemical condition and previous findings, for the entire duration of the immunosuppressive treatment.

Pre-emptive CMV reactivation will be treated by standard treatment for immunosuppressed patients (i.e. ganciclovir or foscarnet). Immunosuppression reduction or discontinuation can be considered depending on severity.

EBV reactivation will be treated with immunosuppressive drug reduction or discontinuation and/or anti-CD20 (Rituximab) depending on the copy level and patient's clinical condition.

Recurrent episodes of CMV reactivation will be addressed with reduction of the immunosuppressive drug tacrolimus. Immunosuppression discontinuation will be considered depending on severity.

Bacterial infection will be treated according to standards. Repeated infections will be addressed by reduction or discontinuation of immunosuppression depending on site of infection, severity and patient's condition.

The safety profile related to concomitant medication will be assessed through general physical examination, neurological visit and through blood examination specifically hematology and chemistry parameters. At every visit signs and symptoms of possible infective events will be recorded.

For all the concomitant medication and procedure used in the protocol only AEs exceeding the grade 3 of severity according to the international definition of AEs will be reported (see also CTCAE).

**5.5.2.1 Documentation of (serious) AE**

Between screening and last follow-up visit the patient will be asked and examined by the investigator for the occurrence of AEs. All AEs will be documented using CTCAE terms (see Appendix), including

- Severity (listed under)
- Onset date
- Stop date
- Causality assessment with study drug
- Action taken
- Outcome

The severity of AEs is defined as (see also CTCAE):

- Grade 1 mild
- Grade 2 moderate
- Grade 3 severe
- Grade 4 life-threatening
- Grade 5 death

All clearly related signs, symptoms and abnormal diagnostic procedures should be grouped together and recorded as a single term in the CRF.

**5.5.2.2 Forwarding**

All the Serious AE (SAE) and the ADR will be notified, as specified in Table 2.

	Documentation	Report	Time
Serious (AE, ADR)	Patient's chart CRF SAE-Form	Investigator forwards SAE-form to Local E.C.	Within 24 h
Non-serious (AE, ADR)	Patient's chart	-	-

Table 2 – SAE/ADR timeline

**5.5.3 Adverse Drug Reaction (ADR)**

An Adverse reaction (ADR): all untoward and unintended responses to an investigational medicinal product related to any dose administered. The phrase responses to an investigational medicinal product means that a causal relationship between the investigational medicinal product and an adverse event is at least a reasonable possibility, i.e. the relationship cannot be ruled out.

### 5.5.3.1 Attribution Definitions

**Not related:** An adverse event that is not related to the use of the investigational product.

**Doubtful:** An AE for which an alternative explanation is more likely, e.g., concomitant drug(s), concomitant disease(s), or the relationship in time suggests that a causal relationship is unlikely.

**Possible:** An AE that might be due to the use of the investigational product. An alternative explanation, e.g., concomitant drug(s), concomitant disease(s), is inconclusive. The relationship in time is reasonable; therefore, the causal relationship cannot be excluded.

**Probable:** An AE that might be due to the use of the investigational product. The relationship in time is suggestive (e.g., confirmed by de-challenge). An alternative explanation is less likely, e.g., concomitant drug(s), concomitant disease(s).

**Very likely:** An AE that is listed as a possible adverse event reaction, and cannot be reasonably explained by an alternative explanation, e.g., concomitant investigational drug(s), concomitant disease(s). The relationship in time is very suggestive (e.g., it is confirmed by de-challenge and re-challenge).

### 5.5.4 Serious adverse event (SAE) or Serious Adverse Reaction (Serious ADR)

SAE or SAR: any untoward expected medical occurrence or effect that at any dose results in death, is life-threatening, requires hospitalisation or prolongation of existing hospitalisation, results in persistent or significant disability or incapacity, or is a congenital anomaly or birth defect.

### 5.5.5 Unexpected adverse reaction (UAR)

UAR: an adverse reaction, the nature or severity of which is not consistent with the applicable product information (e.g. investigator's brochure for an unauthorised investigational product or summary of product characteristics for an authorised product).

### 5.5.6 Suspected unexpected serious adverse reaction (SUSAR)

SUSAR: an adverse event assessed as serious and unexpected and for which there is a reasonable suspected causal relationship with an investigational medical product.

### 5.5.7 Pharmacovigilance Procedure

**Serious Adverse Event:** The Investigator shall report all SAE immediately to the Sponsor and Ethics Committee. The Investigator must fill the SAE report no later than 15 days. For reported deaths of a subject, the Investigator shall supply the Sponsor and Ethics Committee with any additional information requested.

**Suspected Unexpected Serious Adverse Reaction (SUSAR):** In case of a Serious ADR that is unexpected, the Investigator/Sponsor must report the reaction as soon as possible (and in any case no later than 7 days for reactions that are fatal or life-threatening, and no later than 15 days for all other SUSARs) to the competent Regulatory Authorities and to the competent Ethics Committee (and that relevant follow-up information is subsequently communicated within an additional eight days).

**Periodic reporting:** Once a year throughout the trial, the Investigator should provide to Competent Regulatory Authorities and the Ethics Committee an Annual Safety Report, that is, a listing of all suspected Serious ADRs, which have occurred over this period and a report of the subjects' safety.

**Adverse event recording:** All AEs/ADRs regardless of seriousness or relationship to Medicinal Product or expectedness are to be recorded on the corresponding page(s) included in the Case Report Form. Whenever possible, symptoms should be grouped as a single syndrome or diagnosis. The Investigator should specify the date of onset, maximal intensity, action taken with respect to

Medicinal Product, corrective therapy given, outcome and his/her opinion as to whether there is a reasonable possibility that the event was caused by the study Medicinal Product.

The investigator shall keep detailed records of all adverse events, which are reported. These reports must be provided to the competent Authorities if they so request.

### 5.5.8 Follow-up of AE / SAE / ADR

The Investigator should take all appropriate measures to ensure the safety of the patients, notably he/she should follow up the outcome of any event (clinical signs, laboratory values or other, etc.) until the return to normal or until consolidation of patient conditions.

In the case of any **Serious Adverse Event or Serious Adverse Drug Reaction**, the patient must be followed up until clinical recovery is complete and laboratory results have returned to normal, or until progression has been stabilized. This may imply that follow-up will continue after the patient left the study and if the Ethical Committee requests additional investigations.

### 5.5.9 Pregnancy

Pregnant and lactating women will not be included in the study. Females must have a negative pregnancy test prior to be included in the study and will be required to use a reliable and effective form of birth control during the study. Male participants will also be required to prevent pregnancy in their partners. The birth control methods which may be considered effective are: abstinence, oral contraceptives either combined hormonal or progestogen alone, injectable progestogen, subcutaneous contraceptive implants of etonogestrel or levonorgestrel, estrogenic vaginal ring, percutaneous contraceptive patches, intrauterine device or system (IUD) that has a certified failure rate less than 1% per year, male partner sterilization only with the declaration that he is the sole partner, male condoms combined with a female diaphragm either with or without a vaginal spermicide.

The birth control methods which are considered unacceptable in clinical trials are: periodic abstinence (calendar, symptothermal, post-ovulation methods), withdrawal (coitus interruptus), spermicides only, and lactational amenorrhoea method (LAM). For information refer to guidelines

[http://www.hma.eu/fileadmin/dateien/Human\\_Medicines/01\\_About\\_HMA/Working\\_Groups/CTFG/2014\\_09\\_HMA\\_CTFG\\_Contraception.pdf](http://www.hma.eu/fileadmin/dateien/Human_Medicines/01_About_HMA/Working_Groups/CTFG/2014_09_HMA_CTFG_Contraception.pdf)

At every study visit the sexual activity of participants of reproductive age will be re-assessed. If a subject who was previously sexually inactive becomes sexually active, s/he will be counseled about the need to use a reliable and effective form of birth control. Female subjects of childbearing potential will also be required to undergo pregnancy tests at regular intervals, including and especially prior to hNPCs administration. Women who had a positive pregnancy test will not be treated with hNPCs.

All pregnancies that are identified during the study must be followed to conclusion and the outcome of each must be reported. The investigator should be informed immediately of any pregnancy whether occurring in a female participant or the female partner of a male participant. The investigator should report all pregnancies to Sponsor within the same timeframe (24 hours) as SAEs, using the SAE report form. Monitoring of the participant should continue until the conclusion of the pregnancy, and a follow-up SAE report form detailing the outcome of the pregnancy should be submitted to the Sponsor.

## 5.6 Research criteria

In order to gather preliminary information on the efficacy of the experimental treatment clinical and MRI parameters will be recorded throughout the study.

We will evaluate:

- the proportion of disability progression-free patients at week 96;
- the longitudinal changes from baseline to visit week 96 in T25FW, 9-HPT, SDMT

Disability in MS is commonly measured by the Expanded Disability Status Scale (EDSS). The EDSS is based on a standard neurological examination, incorporating seven functional systems (visual, pyramidal, cerebellar, brainstem, sensory, bowel and bladder and cerebral) rated and stored as functional system scores (FSS). Each FSS is an ordinal clinical rating scale ranging from 0 to 5 or 6. These ratings are then used in combination with ambulation capacity to determine the EDSS score that ranges from 0 (normal) to 10 (death due to MS).

Sustained disability progression is defined as an increase of  $\geq 0.5$  EDSS points in the last 12 months. This change has not to be attributable to another etiology (i.e. fever, concurrent illness, MS relapse or concomitant medication) and has to be confirmed at a regularly scheduled visit after at least 12 weeks after the initial disease progression.

Brain MRI parameters: MRI is a useful tool for monitoring MS lesions. Different MRI derived parameters are used to assess paraclinical evidence of drug efficacy.

The following MRI parameters will be evaluated to address the research objective:

- brain and spinal cord atrophy as defined by percentage in brain and spinal cord volume change from baseline to week 96;
- number of new T2 brain and number of spinal cord lesions and changes in T2 lesion volume at week 96;
- number of new T1 hypointense lesions and changes in T1 hypointense lesion volume between baseline and week 96;
- total Gd-enhancing lesions in the brain and spinal cord MRI between baseline and week 96;
- other MR parameters including thalamic, cortical, white matter and normal appearing brain tissue average magnetization transfer ratio (MTR) – ancillary sub-study-.

- Multimodal Evoked Potentials are useful for the evaluation of sensory, motor and visual pathways; Motor Evoked Potentials (MEP), Visual Evoked Potentials (VEP) and Sensory Evoked Potentials (SEP) will be performed at screening, at six and 12 months follow-up and then at two years follow-up (week 24, 48 and 96). We will evaluate changes in amplitude and velocity conduction of MEP, SEP and VEP between the baseline and week 96.

- Optical coherence tomography (OCT) is a useful tool, especially in the field of research, to measure retinal nerve fiber layer (RNFL) thickness as a marker of axonal loss and to detect neurodegeneration in vivo and in a non-invasive way. OCT will be performed at screening, at six and 12 months follow-up and then at two years follow-up (week 24, 48 and 96). We will evaluate RNFL thickness changes between the baseline and week 96.

- to determine immune response in patients treated during immunosuppressive therapy with FK506, cellular and humoral immunological assays will be performed. Immune reconstitution by PB immunophenotyping (lymphocyte subpopulations) will be obtained on blood at screening, at weeks 4th, 12th, 24th, 48th and 96th.

- We will collect data on donor-recipient chimerism on blood samples and CSF (approximately at screening, at weeks 4th and 12th; further evaluations only if clinically useful) with ddPCR assays. It will be performed using the Bio-Rad QX100 system.

- A dosage of tacrolimus on CSF will be performed at week 12th to collect data of CNS drug delivery.

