## 6 Study Enrolment and Withdrawal

### 6.1 Inclusion criteria

1. Signature of the informed consent by the patient or patients' legal tutors
2. Age 18 to 55 years
3. Diagnosis of
  - a. Progressive MS as per the revised MC Donald 2010 criteria with a progressive course according to 2013 Lublin phenotypes classification (PMS) with failure or intolerance to all approved therapies according to the disease course or without any alternative approved therapy
4. Evidence of progression of disease defined by an increase of  $\geq 0.5$  EDSS points in the last 12 months
5. Disease duration 2 to 20 years (included)
6. EDSS  $\geq 6.5$
7. Presence of oligoclonal band in the CSF is required for Primary Progressive MS

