### 8.3 Study Procedure and Study Flow-chart

#### 8.3.1 Enrolment phase

Is the process of informed consent signature (described in the ethical consideration chapter). Starting from the signature of the informed consent by the patient or patients' legal tutors, the subjects will be enrolled in the clinical trial. When the enrolment is confirmed the patient screening number will be assigned consecutively in increasing order starting with '001'. The list will be filed with the investigator's file. After the enrolment of a patient in the study, the investigator sends the enrolment module to the principle investigator by fax or email to clinical research monitor.

Those protocol phases are foreseen after signature of the informed consent:

- **Screening/baseline phase**, during which the conditions required by the clinical protocol for patients' inclusion/exclusion will be assessed (screened subject). The duration will be of three weeks (+/- 3 working days). At the end of the screening phase, the inclusion/exclusion criteria of the study will be evaluated (enclosed subject).
- **Pre-treatment phase**: carried from the end of the screening phase to the day before the start of treatment.
- **Treatment phase**: The intrathecally administration of hNPCs will be performed on day 0. Prophylactical treatment with Tacrolimus will be performed for 96 weeks starting from day -7 whereas oral corticosteroids will be administered for the first 4 weeks.
- **Follow-up phase**: 96 weeks after the experimental drug administration day 0.

At the end specify if the end of total follow-up or single patient follow-up.

At the end of the total follow-up, for all patients enrolled and treated in the study is planned a long term follow up, in accordance with the national applicable laws and the international guidelines.

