### 8.3.3 Pre-treatment phase

This phase will start after the ending of all the procedure of the screening/baseline phase and it will end the day before the treatment phase (day-1):

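### The week-96 progression-free endpoint uses a 12-month look-back with no named study reference EDSS, so one sentence supports materially different results

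*Combined protocol and SAP*

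**What the plan says.** Section 5.6 (Research criteria) lists "the proportion of disability progression-free patients at week 96" among the measures meant to give preliminary information on efficacy. It defines sustained progression as an increase of at least 0.5 "EDSS points in the last 12 months. This change has not to be attributable to another etiology". The change "has to be confirmed at a regularly scheduled visit after at least 12 weeks after the initial disease progression". No visit is named as the EDSS reference, in section 5.6 or elsewhere.

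The 12-month limit also appears in inclusion criterion 4 of section 6.1 ("Evidence of progression of disease defined by an increase of" at least 0.5 points), where it describes the year before entry. Most neighbouring endpoints in section 5.6 run from baseline, for example "the longitudinal changes from baseline to visit week 96 in T25FW, 9-HPT, SDMT" and "changes in T1 hypointense lesion volume between baseline and week 96".

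EDSS is rated twice before dosing: at screening (section 8.3.2) and on day -1 (section 8.3.3). Section 8.3.1 calls the first of these periods the "Screening/baseline phase", and section 8.3.3 starts pre-treatment "after the ending of all the procedure of the screening/baseline phase". After dosing, section 8.3.5 schedules EDSS at weeks 4 and 12 and then at every 12-weekly visit to week 96. Section 11 plans descriptive statistics and leaves detailed methods to a SAP still to be written.

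**The concern.** A look-back that makes sense for eligibility has been carried into an outcome definition. At entry it asks whether the patient worsened in the year before the study. At week 96 the same words ask only about the second year of follow-up, while the endpoint's name suggests the whole 96 weeks. The sentence can also be read as a rule applied at every visit, which behaves differently.

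The trial is open label and uncontrolled (section 5.1), so this proportion can only be judged against outside expectations. A figure that moves by tens of percentage points with the reading of one sentence is hard to use for that purpose.

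**Working it through.** **No figure to reproduce.** The documents give no progression rate, target or precision for this endpoint.

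**Inputs from the documents**
- EDSS visits: pre-dose, then weeks 4, 12, 24, 36, 48, 60, 72, 84 and 96 (sections 8.3.2, 8.3.3, 8.3.5).
- Confirmation at least 12 weeks later at a scheduled visit (section 5.6). The last confirmable onset is week 84, since 84 + 12 = 96.
- Section 5.6 equates 12 months with week 48 and two years with week 96 (evoked potentials and OCT). The 12 months before week 96 therefore start at week 48, where EDSS is scheduled.
- At most 24 patients (section 8.1). With three per cohort and no expansion, 4 × 3 = 12 (section 7.10).

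**Step 1: a permanent rise of 0.5, by the visit where it is first seen**

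| First seen | Pre-dose reference | Week-48-to-96 window | Rolling look-back, within study |
|---|---|---|---|
| Weeks 4, 12, 24, 36 | progression | progression-free | progression |
| Week 48 | progression | progression-free if week 48 is the reference | progression |
| Weeks 60, 72, 84 | progression | progression | progression |
| Week 96 | not confirmable | not confirmable | not confirmable |

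For example, a rise seen at week 24, confirmed at week 36 and still present at week 96 is no change between weeks 48 and 96.

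**Step 2: size, as an illustration.** Assume true 96-week progression P of 30, 50 or 70%, a constant hazard of lasting 0.5-point steps, and error-free EDSS. With λ = −ln(1 − P)/96 per week and S(t) = exp(−λt):

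- Pre-dose reference, onset by week 84: S(84) = 0.732 / 0.545 / 0.349.
- Week-48 window, repeat steps possible: S(36) = 0.875 / 0.771 / 0.637, because 84 − 48 = 36 weeks are at risk.
- Week-48 window, one step only: 1 − [S(48) − S(84)] = 0.895 / 0.838 / 0.801.

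Difference from the pre-dose reference, in percentage points:
- P = 30%: 14.3 to 16.3
- P = 50%: 22.6 to 29.3
- P = 70%: 28.8 to 45.2

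In patients, that is 3.4–3.9, 5.4–7.0 and 6.9–10.9 of 24, or 1.7–2.0, 2.7–3.5 and 3.5–5.4 of 12.

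**Step 3: the rolling reading.** With error-free EDSS and no look-back before dosing, it equals the pre-dose rule: 73/55/35%. A simulation then made each rating independently wrong by half a point with probability 10% (assumed):

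| Rule | P = 30% | P = 50% | P = 70% |
|---|---|---|---|
| Pre-dose reference | 70% | 53–54% | 35–37% |
| Rolling, earliest rating in the window as reference | about 60% | about 45% | about 30% |
| Rolling, lowest rating in the window as reference | 48% | 36% | 23% |

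The fall depends strongly on which rating in the window serves as reference, and the plan does not say. If an early look-back also reached before dosing, it would meet the rise of at least 0.5 that inclusion criterion 4 requires, and lower the proportion further.

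**The case against.** The strongest objection is that the sentence need not be read as a single test at week 96. It describes an event with an onset and a later confirmation, section 5.6 has parameters recorded throughout the study, and EDSS is scheduled at every main visit. All of this fits visit-by-visit assessment, under which the week-24 example is progression. A one-off test at week 96 fits the confirmation clause poorly, because no scheduled visit follows at least 12 weeks later. This stands, and it makes the week-48-to-96 result conditional. It does not settle the definition: the plan does not state the rolling rule, and that rule leaves the reference undefined and open to rating error.

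A reader might infer that the endpoint is biased in the product's favour. The documents do not support that as a general statement, since the week-96 reading raises the proportion and the rolling reading lowers it. Nor is it right that no EDSS is scheduled at the start of the window: by the protocol's own convention that is week 48, and EDSS is rated then.

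It is also fair that the rates are assumptions, that 24 patients is a ceiling, that the endpoint is exploratory, and that the SAP could still repair the definition. These limit the weight of the point, but nothing in section 11 commits the SAP to the repair.

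**Conclusion.** The point holds conditionally. The 12-month limit and the absence of a named reference are plain in section 5.6, and the sentence supports materially different results. If applied at week 96 as worded, lasting, confirmed rises first seen at weeks 4 to 36 count as progression-free. The proportion is then about 14 to 45 points higher than with a pre-dose reference, under the assumed 30–70% progression, constant hazard and error-free ratings. If applied as a rolling look-back, early rises are caught, but rating error pushes the proportion down.

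The documents do not show which reading the sponsor intends, so it would go too far to say that first-year worsening will be counted as progression-free. The matter should be corrected, but it concerns a descriptive research endpoint only. The primary safety endpoints and dose escalation are unaffected.

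**What to change.** In section 5.6, remove the 12-month limit from the progression definition; inclusion criterion 4 keeps it. Define progression as an EDSS increase of at least 0.5 from one named pre-dose rating, for example screening, which the protocol already labels as part of baseline. Allow onset at any scheduled EDSS visit after day 0 up to week 84, with confirmation at a scheduled visit at least 12 weeks later.

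Report rises first seen at week 96 separately as unconfirmed. The end of study visit in section 8.3.5 is described as 8 weeks after the end of treatment visit, so if that is week 96 it falls short of the 12 weeks required. The denominator and the layout for missing data can be left to the SAP.

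The cost is wording only, since every EDSS visit needed is already scheduled. The downside is that the reported proportion will be less favourable than under the week-96 look-back.

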  - Week 96 abdominal ultrasound.

- Administration of MsQuol54 will be performed at 24, 48 and 96 weeks.
- Brain and spinal cord MRI with gadolinium: will be performed at 12, 24, 48 and 96 weeks.
- Cerebrospinal fluid examination (CSF): a CSF examination will be performed 12 weeks  $\pm$  2 weeks after hNPCs administration.

All new or worsening neurological signs and symptoms will be monitored, evaluated and recorded.

In the presence of newly identified or worsening of neurological sign or symptom the investigator should assess whether the patient is experience a relapse of MS, any neurological disorder related to the recent injection procedure or any other neurological (non-MS related) disorder.

The following procedure might be performed, at investigator discretion, in the presence of a new or worsening neurological or systemic condition:

- Haematology and biochemistry examination complete of ESV e CRP
- Chest X ray
- Brain and spinal cord MRI with gadolinium
- Lumbar puncture
- EKG

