#### AEs related to the use of tacrolimus:

The most common adverse events reported with use of tacrolimus are listed below.

Nervous System: very common (**frequency >10**): headache and tremors. Common (> 1:100 < 1/10): paresthesias or dysesthesias mental status changes, seizures, encephalopathy, dizziness, impaired writing, and peripheral neuropathy. Late neurotoxicity was highly associated with severe infections and multi-organ failure.

Respiratory System: common: pleural effusion, dyspnea, lung disorders, cough, pharyngitis rhinitis and sinusitis.

Renal System: very common: renal function impairment; common: renal insufficiency acute renal failure oliguria, nephrotoxicity, kidney tubular necrosis, urinary disturbances.

Psychiatric Symptoms: very common: insomnia; common: nightmares, depression, irritability, agitation, anxiety, hallucinations, abnormal dreams.

Immunologic System: Immunologic side effects have included infectious complications as a result of immunosuppression. Cytomegalovirus is the most frequently encountered viral pathogen in patients treated with tacrolimus. Bacterial infections, primarily gram-positive and gram-negative aerobes, and fungal infections are also encountered. Progressive multifocal leukoencephalopathy (PML) related to a JC virus infections have been reported.

Hematologic System: common: anemia, leukopenia, leukocytosis, thrombocytopenia hematocrit alterations.

Cardiovascular system: very common: hypertension; common: tachycardia hemorrhage, myocardial infarction, thrombosis, hypotension, phlebitis.

Gastrointestinal system: very common: diarrhea, nausea; common: elevations in liver function tests cholangitis cholestatic jaundice hepatitis gastrointestinal hemorrhage stomatitis, gastrointestinal perforation.

Metabolic adverse events: very common: hyperkalemia, hyperglycemia, diabetes mellitus; common: hypomagnesemia, hypokalemia, hyperlipidemia, acidosis, hypocalcemia, hypophosphatemia, hyponatremia, anorexia.

Oncologic adverse events: in one study of 936 transplant patients receiving tacrolimus as primary immunosuppressive therapy, post transplant lymphoproliferative disease (PTLD) occurred in 15 (1.6%) patients. Serologic evidence of Epstein-Barr virus infections was found in all 15 patients. Oncologic side effects, or the development of new malignancies, are of particular concern

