#### 7.10 Methods of assigning patients to treatment groups

The protocol will consist of a total of four TC (from A to D), each of which receiving a single escalating dose of hNPCs injected intrathecally as it follows:

- TC-A:  $0.7 \times 10^6 \pm 10\%$  cells/kg of body weight;
- TC-B:  $1.4 \times 10^6 \pm 10\%$  cells/kg of body weight;
- TC-C:  $2.8 \times 10^6 \pm 10\%$  cells/kg of body weight;
- TC-D:  $5.7 \times 10^6 \pm 10\%$  cells/kg of body weight.

The trial will start with TC-A and will go through the subsequent enrolment of patients to be included in TCs from B to D.

Each cohort will consist of three patients at minimum. However in case of safety issue the numerosity of each TC will be increased to six patients, as explained below.

We define a DLT any adverse event of grade 3 possibly related to hNPCs or to the procedure. However we will not consider a DLT a prolonged hospitalization due to post lumbar puncture headache if not associated to any meningeal sign. We will not considered DLT adverse events related to concomitant treatments (tacrolimus and steroids)

After the inclusion of the first patient of the TC we will wait at least 14 days to treat the second patient. The same interval time will be used for all the further patients within the same TC. After the inclusion of all the planned patients within a TC, we will wait at least 3 months after the inclusion of the last patient before switching to the higher TC.

In case of none DLT within the TC, we will wait at least 3 months after the inclusion of the last patient and then we will move to the higher TC.

In case of 1 DLT within the TC, the cohort will be extended to 6 patients. If another DLT will be observed, the current dosage will be considered excessive and the immediate lower dosage will be considered MTD.

The safety monitoring board will review all safety data in the case of an AE  $\geq 3$  evaluated “possibly related to hNPC” by investigators and in any case before the shifts between TCs.

This will be repeated for every TC up to the end of the study.

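### Confirmed EDSS worsening attributed to the protocol's own immunosuppression, or to relapse, does not count as progression, so the week-96 progression-free proportion tends to be too high

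*Combined protocol and SAP*

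**What the plan says.** Section 5.6 lists, among its research measures, "the proportion of disability progression-free patients at week 96". Its stated purpose is: "In order to gather preliminary information on the efficacy of the experimental treatment clinical and MRI parameters will be recorded throughout the study".

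Sustained progression is an EDSS increase of at least 0.5 points that meets two further conditions. The first is attribution: "This change has not to be attributable to another etiology (i.e. fever, concurrent illness, MS relapse or concomitant medication". The second is that the change "has to be confirmed at a regularly scheduled visit after at least 12 weeks after the initial disease progression".

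The mandated immunosuppression falls under concomitant medication in the protocol's own usage. Section 7.10, defining dose-limiting toxicity (DLT), says: "We will not considered DLT adverse events related to concomitant treatments (tacrolimus and steroids". Section 7.11 defines concomitant therapy to cover every drug given between consent and the end-of-study visit. Section 8.3.1 says: "Prophylactical treatment with Tacrolimus will be performed for 96 weeks starting from day -7". Section 5.5.2 lists these nervous-system effects of tacrolimus as common: "paresthesias or dysesthesias mental status changes, seizures, encephalopathy, dizziness, impaired writing, and peripheral neuropathy".

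Progression-free is not defined separately. Section 11 promises descriptive statistics and leaves detailed methods to a SAP still to be prepared.

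**The concern.** An attribution clause of this kind does little harm where background drugs are incidental. Here one of those drugs is part of the regimen and is planned for the whole endpoint window. A confirmed EDSS rise that the investigator puts down to tacrolimus fails the progression definition. Unless another rule intervenes, that patient counts as a success in a figure meant to give early efficacy information.

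Relapse works the same way. Every patient enters at EDSS 6.5 or above (6.1). For a baseline of 5.5 or above, the relapse definition in 8.3.5 needs a 0.5-point EDSS change with functional-system changes, and it sets no maximum duration. The progression threshold is also 0.5 points, so one lasting step can be labelled either way.

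The trial is open label and has no control group (5.1), so the attribution is made with treatment known and there is no comparison arm in which the effect could cancel.

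**Working it through.** **Which causes the clause removes**

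- *Tacrolimus and steroids:* removed. Section 5.6 names concomitant medication, and 7.10 puts both drugs in that class. Oral steroids run for about four weeks, so tacrolimus is the one that matters at week 96.
- *MS relapse:* removed by name. An independent rater scores the EDSS at a suspected relapse, but the treating physician first judges whether the event fits the definition (8.3.5).
- *hNPCs and the injection procedure:* unclear. Neither is in the list in 5.6, and 7.10 keeps both apart from concomitant treatments. They are removed only if another etiology is read as any cause other than MS progression. Section 5.5.1 makes that reading possible, because the investigator must separate relapse from "any neurological disorder related to the recent injection procedure or any other neurological (non-MS related) disorder". But that is a safety instruction and not part of the progression rule.

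**What confirmation leaves for the clause to act on.** Twelve-week confirmation already screens out most fever and short illness. What the attribution clause removes in addition is largely worsening that persisted. Some of this may be a reversible drug effect that lasts because dosing continues.

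**Denominators.** The plan's maximum reproduces: 4 cohorts × 6 = 24. The minimum, if all four doses are completed without expansion, is 4 × 3 = 12.

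**Shift per patient.** If a patient with excluded worsening is scored progression-free, the proportion rises by 1/N.

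| N | Source | 1/N, points |
|---|---|---|
| 24 | maximum | 4.2 |
| 12 | four cohorts of three | 8.3 |
| 6 | expanded cohort | 16.7 |
| 3 | minimum cohort | 33.3 |

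These are upper limits. If the patient is dropped from the denominator instead, x/N becomes x/(N − 1), a rise of x/[N(N − 1)], which cannot exceed 1/N because x is at most N − 1. If the patient also has progression attributed to MS, the shift is zero.

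**Chance of at least one such patient.** Let q be the probability that a patient has confirmed worsening attributed only to an excluded cause. The documents give no value, so the q below are assumptions. P(at least one) = 1 − (1 − q)^N.

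| q (assumed) | N = 24 | N = 12 |
|---|---|---|
| 2% | 38% | 22% |
| 5% | 71% | 46% |
| 10% | 92% | 72% |

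**Illustration.** Assume 12 of 24 patients have confirmed worsening from any cause, and 2 of those 12 are attributed elsewhere (Clopper-Pearson 95% intervals).

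- All worsening counted: 12/24 = 50.0% (29.1 to 70.9).
- The 2 scored progression-free: 14/24 = 58.3% (36.6 to 77.9).
- The 2 dropped: 12/22 = 54.5%.

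The same data thus give three answers, and the plan does not choose among them.

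**The case against.** The best case for the plan has four parts.

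**The harm is measured elsewhere, and at higher rank.** Neurological change is a primary safety endpoint in all three periods of 5.3, and the long-term item carries no attribution limit. Section 5.5.7 has all adverse events recorded. The T25FW, 9-HPT and SDMT changes in 5.6 have no attribution clause. This stands: a reader might infer that regimen harm disappears from the trial, and the documents do not support that. One qualification is needed. For concomitant medication and procedures, 5.5.2 limits reporting to events above grade 3. That conflicts with 5.5.7, and the two must be reconciled. Even full safety capture would not correct the efficacy proportion.

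**The clause is a choice of estimand.** Section 5.4 seeks preliminary data on the effect of hNPCs, and setting aside drug effects and relapse is a defensible definition of disease progression. This stands as a reason to keep the restricted version. It is not a reason to report that version alone.

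**The cells and the procedure are not named.** A reader might infer that disability caused by the graft or the injection is scored as progression-free. The text does not say so. Nor does it say that any excluded patient is progression-free; censored or non-evaluable status is equally open.

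**The size is unknown.** A reader might take the common frequency band for tacrolimus (between 1 in 100 and 1 in 10) as the rate of misclassification. That band describes adverse events, not confirmed EDSS rises. Section 7.2 makes tacrolimus conditional on tolerance, tapers it and allows it to be reduced or stopped. Entry requires recent EDSS worsening (6.1), so some affected patients may also progress from MS and already be events. No fixed overstatement in points can be defended.

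**Conclusion.** The concern holds for the mandated immunosuppression and for relapse. As written, confirmed worsening attributed to either is not progression, and the natural complement, the progression-free proportion at week 96, is biased upward. For hNPCs and the procedure the finding is an ambiguity to be closed, not an explicit exclusion.

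The size is at most 4.2 points per affected patient at N = 24, 8.3 at N = 12 and 33 in a cohort of three. It rests on two conditions: that excluded patients are scored progression-free, and that they have no MS-attributed progression as well. The number of such patients cannot be taken from the documents.

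At these sample sizes the shift from one or two patients lies well inside the sampling interval, but it acts in one direction. It affects a descriptive research endpoint. It does not affect the primary safety assessment, or dose escalation, which 7.10 bases on DLTs.

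**What to change.** In 5.6 and in the SAP still to be written:

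1. State that confirmed EDSS worsening attributed to hNPCs, the procedure or protocol-mandated immunosuppression counts as an event.
2. Report the proportion free of confirmed EDSS worsening from any cause alongside the attribution-restricted version.
3. Define progression-free. State that patients with excluded worsening stay in the denominator, and say how they are classified.

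No new data are needed: 8.3.5 already schedules EDSS at weeks 4 and 12 and at every scheduled visit after that. The cost is a few sentences and one table row. The downside is that the reported progression-free proportion may be lower.
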